**Table 7.1 Dose Delays/Reductions for Drug-Related Toxicity**

Event Grade	Action
Grade 1 or 2, including significant increase in LFTs (as assessed by the Investigator) and alopecia	Continue current dose level, unless dose interruption/modification may be clinically indicated, e.g., due to significant increase in LFTs
Grade 3-4 nausea, vomiting or diarrhea lasting < 24 hours	Withhold ARQ 087 until recovery to Grade 1 or baseline. If recovery occurs within 24 hours, restart ARQ 087 at the current dose level.
Grade 3-4 toxicity, including nausea, vomiting or diarrhea lasting $\geq$ 24 hours	
Withhold ARQ 087 until recovery to Grade 1 or baseline.
 
 
- If recovery occurs within 14 days, restart ARQ 087 at the dose and schedule of the previous cohort for all subsequent cycles, unless further dose reduction is required.
 
- If recovery occurs within 21 days of the drug hold, ARQ 087 may be restarted upon agreement between the Investigator and the Sponsor's Medical Monitor. Treatment should be restarted at the dose and schedule of the previous cohort for all subsequent cycles, unless further dose reduction is required.
 
- If recovery occurs after more than 21 days of the drug hold, ARQ 087 should be permanently discontinued
 

**Table 7.2 ARQ 087 Dose Reduction Schema**

Current Dose	Dose after Reduction
Dose Level 1: 3 capsules qd (300 mg daily)	Dose Level 2: 2 capsules qd (200 mg daily)
Dose Level 2: 2 capsules qd (200 mg daily)	Dose Level 3: 1 capsule qd (100 mg daily)
Dose Level 3: 1 capsule qd (100 mg daily)	

## 7.4 Treatment Compliance

A subject is considered compliant with the study protocol when study medication is administered at a compliance level of  $\geq 80\%$ . In order to evaluate the safety of ARQ 087, replacement of non-compliant subjects will be allowed during Cycle 1 of Treatment Period 2/Continuous Dosing.

Compliance will be calculated using the following equation:

(Number of capsules actually ingested / number of capsules that should have been ingested per dose level) x 100 = % compliance

## 7.5 Blinding

This is an open-label study. Neither the subject nor the Investigator and site staff will be blinded to the treatment administered.

## 7.6 Prior Treatment

Reasonable efforts will be made to determine all relevant prior treatments received by the subject within 30 days prior to the first ARQ 087 dose. All relevant information must be recorded on the appropriate subject's electronic case report form (eCRF). All surgical procedure history, prior chemotherapy, and radiation therapy must be recorded on the appropriate eCRF.

## 7.7 Concomitant Treatments

All information regarding concomitant treatments (medications or procedures) must be recorded on the subject's eCRF (including the name of the medication or procedure and duration of treatment). Complete information of analgesic consumption should be obtained and recorded.

### 7.7.1 Permitted Treatment

Palliative and supportive care for disease-related symptoms will be offered to all subjects.

In addition, the following treatments are allowed:

- Standard therapies for concurrent medical conditions
  - If active hepatitis B virus (HBV) replication is discovered, the subject must be immediately treated with conventional anti-viral therapy (excluding interferon) per standard of care

- Erythropoietin Stimulating Agents (ESA): Please follow the American Society of Clinical Oncology (ASCO), the American Society of Hematology, MEDICARE guidelines for the use of epoetin in subjects with cancer and FDA alerts dates 09 March 2007, 08 November 2007, 12 March 2008, 31 July 2008, and 02 December 2008.
- Hematopoietic growth factors, including filgrastim (Neupogen®), or other granulocyte colony stimulating factors (G-CSF). Please follow ASCO guidelines for the use of white blood cell growth factors. <http://jco.ascopubs.org/content/24/19/3187.full>
- Prophylactic antiemetics may be administered according to standard practice
- Megestrol acetate (Megace®)
- Use of topical corticosteroids, topical and systemic antibiotics according to SOC or institutional guidelines

### 7.7.2 Prohibited Treatment/Treatment to Be Avoided or Used with Caution

The following treatments are not allowed during the study:

- Any concurrent anti-cancer therapy including chemotherapy, radiotherapy, hormonal, targeted therapy, or immunotherapy
  - Palliative radiotherapy for local pain-control may be allowed, provided the subject does not meet criteria of progressive disease and treated lesions will not be included in the target/non-target lesion assessment
- Other investigational agents
- Immunosuppressive therapies, including systemic corticosteroids (except up to a 25 mg/day prednisone-equivalent dose or when used intermittently in an antiemetic regimen, for CNS metastases management or as premedication for imaging studies)

The following treatments should be avoided, if possible or used with caution during the study:

- ARQ 087 may inhibit CYP1A2 or CYP2D6 metabolism, hence co-administration of ARQ 087 with drugs known to be substrates of CYP1A2 or CYP2D6 should be avoided or used with caution (see Appendix 4)
- ARQ 087 may be a substrate and inhibitor of human P-glycoprotein (P-gp), therefore co-administration of ARQ 087 with drugs known to be P-gp substrates with narrow therapeutic index should be avoided or used with caution (see Appendix 5)
- Drugs with known liver toxicity, e.g., clotrimazole, should be avoided or used with caution; if such drugs need to be administered, LFT should be done every 4-5 days during the drugs' co-administration

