*A sum of the diameters* (longest for non-nodal lesions, short axis for nodal lesions) for all target lesions will be calculated and reported as the baseline sum of the diameters. If lymph nodes are to be included in the sum, then as noted above, only the short axis is added into the sum. The baseline sum of the diameters will be used as reference to further characterize any objective tumor regression in the measurable dimension of the disease.

All other lesions (or sites of disease) including pathological lymph nodes should be identified as non-target lesions and should also be recorded at baseline. Measurements are not required and these lesions should be followed as ‘present’, ‘absent’, or in rare cases ‘unequivocal progression’ (more details to follow). In addition, it is possible to record multiple non-target lesions involving the same organ as a single item on the case record form (e.g. ‘multiple enlarged pelvic lymph nodes’ or ‘multiple liver metastases’).

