#### **Evaluation of Target Lesions**

- *Complete Response (CR)*: Disappearance of all target lesions. Any pathological lymph nodes (whether target or non-target) must have reduction in short axis to < 10 mm.
- *Partial Response (PR)*: At least a 30% decrease in the sum of diameters of target lesions, taking as reference the baseline sum diameters.
- *Progressive Disease (PD)*: At least a 20% increase in the sum of diameters of target lesions, taking as reference the smallest sum on study (this includes the baseline sum if that is the smallest on study). In addition to the relative increase of 20%, the sum must also demonstrate an absolute increase of at least 5 mm. (Note: the appearance of one or more new lesions is also considered progression).
- *Stable Disease (SD)*: Neither sufficient shrinkage to qualify for PR nor sufficient increase to qualify for PD, taking as reference the smallest sum diameters while on study. In this study, the minimum duration for SD is defined as 8 weeks ( $\pm$  2 days).

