### Missing Assessments and Inevaluable Designation

When no imaging/measurement is done at all at a particular time point, the subject is not evaluable (NE) at that time point. If only a subset of lesion measurements are made at an assessment, usually the case is also considered NE at that time point, unless a convincing argument can be made that the contribution of the individual missing lesion(s) would not change the assigned time point response. This would be most likely to happen in the case of PD. For example, if a subject had a baseline sum of 50 mm with three measured lesions and at follow-up only two lesions were assessed, but those gave a sum of 80 mm, the subject will have achieved PD status, regardless of the contribution of the missing lesion.

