### Frequency of Tumor Re-evaluation

In this study, tumor measurement will be conducted at Baseline, and then in 8-week intervals while the subject is on treatment or as clinically indicated until progression of disease,

withdrawal of consent, death, or loss to follow-up. Tumor measurement will also be performed during the End-of-Treatment visit if it is not done within 28 days of the visit date.

Baseline tumor assessments must be performed within four weeks (28 days) of the first dose of treatment.

All efforts should be made to ensure consistency between the baseline measurements and all subsequent measurements in reference to utilization of scanning methods, equipment, technique (including slice thickness and field of view), and the radiographic interpreter.

The radiological evaluation must include CT or MRI scanning of the chest, abdomen, and pelvis. Any additional suspected sites of disease should also be imaged. All evaluations should meet the standard of care for imaging of lesions in the respective organ(s).

All target and non-target sites are evaluated at each time point of tumor assessment.

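### Section 7.7.2 leaves irradiated lesions out of the tumour assessment, which contradicts Appendix 6, leaves a route to a false partial response and stops counting progression in those lesions

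*Protocol*

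**What the plan says.** Protocol section 7.7.2 bars concurrent anti-cancer therapy but allows palliative radiotherapy for local pain in a subject who has not progressed. It adds that "treated lesions will not be included in the target/non-target lesion assessment".

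Appendix 6 sets the scoring rules that this meets:

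- **Lesion list.** Up to five measurable lesions are targets. For the rest, "All other lesions (or sites of disease) including pathological lymph nodes should be identified as non-target lesions and should also be recorded at baseline".
- **Reference for response.** PR is "At least a 30% decrease in the sum of diameters of target lesions, taking as reference the baseline sum diameters". Nothing provides for recalculating the baseline sum once a lesion is excluded.
- **Completeness.** "All target and non-target sites are evaluated at each time point of tumor assessment". No exception is made for irradiated lesions.
- **Incomplete measurement.** "If only a subset of lesion measurements are made at an assessment, usually the case is also considered NE at that time point". The exception is a convincing argument that the missing lesion would not alter the response. The time-point table also gives NE when target lesions are only partly evaluated, non-targets have not progressed and nothing new has appeared.
- **Confirmation.** None is required for CR or PR.

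Appendix 6 deals with lesions irradiated before baseline (not measurable unless they have since progressed). It has no counterpart for radiotherapy given on study. SAP section 3.2.4 (best overall response, duration, PFS) and section 5.4.5 (target-sum listings, waterfall plot) do not mention on-study radiotherapy.

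**The concern.** Section 7.7.2 takes a followed lesion out of the assessment, while Appendix 6 requires it to be assessed and keeps it in the baseline denominator. The same scan can then be scored PR, SD or NE, depending on which sentence the site or programmer follows. One of those scorings credits the study drug with a fall in the sum that comes only from leaving a lesion out. Separately, a lesion that has been left out can grow without this counting as progression.

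The quantities at stake are ORR, DCR, duration of response and PFS. Two enrolment decisions also depend on tumour size: the 10-subject iCCA look, and the sub-cohort rule based on a reduction of at least 15% at first restaging.

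**Working it through.** **Inputs from the documents.** PR: fall of at least 30% from the baseline sum. PD: rise of at least 20% and at least 5 mm over the smallest sum on study (both Appendix 6). Sub-cohort rule: reduction of at least 15% at C3D1 (Protocol 3 and 4.1.2; SAP 2.2.1). iCCA look at 10 subjects: stop at ≤30% (Protocol section 10), continue at ≥30% (SAP section 7).

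**Assumed.** Lesion sizes, changes in the retained lesions and true response rates. The documents give none of these.

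**1. The plan's own example.** Appendix 6 has a baseline of 50 mm from three lesions and 80 mm from two of them at follow-up, and calls this PD. (80 − 50)/50 = +60% and +30 mm, so PD is reproduced. It is PD whatever the missing lesion does. The example does not cover a missing lesion that makes the sum look smaller.

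**2. Target lesion left out, full baseline kept.** Let w be the excluded lesion's share of the baseline sum and g the relative change in the retained lesions.

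Apparent change = (1 − w)(1 + g) − 1

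This reaches −30% when w ≥ 1 − 0.7/(1 + g).

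| Change in retained lesions (g) | Smallest share w that gives PR |
|---|---|
| +10% | 1 − 0.7/1.1 = 36.4% |
| 0 | 1 − 0.7/1.0 = 30.0% |
| −10% | 1 − 0.7/0.9 = 22.2% |
| −20% | 1 − 0.7/0.8 = 12.5% |

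**3. One scan, three scores.** Target lesions are 40 + 30 + 30 = 100 mm, nothing changes, and one 30 mm lesion is irradiated and left out.

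- Full baseline kept, partial sum used: (70 − 100)/100 = −30%, PR.
- Baseline re-based to the retained lesions: (70 − 70)/70 = 0%, SD.
- Appendix 6 rule for incomplete measurement: the missing lesion could change the response, so NE.

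Only the first is a false response.

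**4. The 15% rule.** With five equal lesions of 20 mm, leaving one out gives (80 − 100)/100 = −20%, past the 15% mark. A further fall in the remainder from 80 to 70 mm (10/80 = 12.5%) reaches PR.

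**5. Non-target lesion left out.** The target sum does not change, so steps 2 to 4 do not apply. The time-point table still allows PR or SD when non-targets are not all evaluated, so unequivocal progression of the excluded lesion is not counted.

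**6. iCCA look.** One responder in 10 is 10 percentage points. Moving from 2/10 to 3/10 crosses the SAP threshold; moving from 3/10 to 4/10 crosses the protocol's. The chance that the count sits exactly one short is C(10,k) p^k (1 − p)^(10 − k):

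| Assumed true ORR | P(exactly 2/10) | P(exactly 3/10) |
|---|---|---|
| 10% | 0.19 | 0.06 |
| 20% | 0.30 | 0.20 |
| 30% | 0.23 | 0.27 |
| 40% | 0.12 | 0.21 |

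These show how often one responder would matter. They are not probabilities that a false PR occurs.

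**The case against.** **Appendix 6 already prevents the false PR.** Section 7.7.2 gives no scoring instruction and does not tell anyone to set a partial sum against the full baseline. Appendix 6 governs scoring, and its rules point to NE when an omitted target lesion could change the response. This largely stands: a false PR needs the lesion omitted, the full baseline kept and the NE rule passed over. The safeguard is not secure, however. The text rule concerns measurements that were not made, and says usually. An irradiated lesion can be measured; section 7.7.2 removes it from the set, so the reduced set can be taken as complete. The NE rule also does nothing for an excluded non-target lesion.

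**The sentence may limit which lesions can be irradiated.** It is worded as a condition: "Palliative radiotherapy for local pain-control may be allowed, provided the subject does not meet criteria of progressive disease and treated lesions will not be included". On that reading no followed lesion is ever dropped. The reading is possible but narrow. Every baseline lesion is target or non-target, and an unequivocal new lesion is progression, which the same sentence excludes. What remains is little more than equivocal new lesions and nodes under 10 mm, which are not recorded.

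**Omission might seem to open the way to CR.** A reader might infer that dropping a non-target lesion removes a bar to CR. The documents do not support this: the table scores target CR with non-targets not evaluated as PR.

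**Efficacy is descriptive.** The primary objective is safety and no hypothesis is tested. The 15% rule looks only at the first restaging, and in the protocol closure is optional. This limits the weight of the point, but response still decides iCCA enrolment.

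**Conclusion.** The concern holds as a contradiction between stated rules. Section 7.7.2 and the completeness requirement in Appendix 6 cannot both be followed, and neither document says which prevails or how the baseline sum is then used. Two consequences follow. There is a conditional route to an unconfirmed false PR, needing an omitted target share of 30% with the other lesions stable and less if they shrink. There is also a direct loss of progression in any irradiated lesion that is left out.

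A reader might infer that the plan produces false responses as a matter of course, or that ORR is inflated by some definite amount. Neither is supported. The NE rules stand against the first. On the second, neither document gives a radiotherapy frequency, and the lesion sizes used here are illustrations. What can be said is that one affected scan sets a subject's best overall response and is worth one responder in the 10-subject iCCA look, which matters only when the count is one short of the threshold. The point should be corrected, but it does not touch the primary safety objective.

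**What to change.** Leave who may receive radiotherapy unchanged. Reconcile the scoring wording in Protocol section 7.7.2, Appendix 6 and SAP section 3.2.4 so that they state one rule:

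- Irradiated lesions stay on the lesion list and continue to be assessed. The baseline sum is not re-based.
- After radiotherapy to a target lesion, a time point cannot be scored CR, PR or SD. It is NE unless PD is shown, and growth of the irradiated lesion itself counts towards PD.
- Disappearance of an irradiated non-target lesion does not support CR. Its unequivocal progression counts as PD.
- The SAP states how PFS treats these NE time points. Section 3.2.4 now accepts an NE scan as the last tumour assessment for censoring, so it should say whether such subjects are censored there or at the last scan before radiotherapy.
- Affected subjects are listed, with radiotherapy date and lesion.

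The cost is wording, and possibly one eCRF field: section 7.7 secures the name and duration of a concomitant procedure, and anatomic site is requested only for previous radiotherapy (section 6.1). A few subjects lose later evaluable time points, and ORR may come out slightly lower.

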## 7.8 Potential Risks for Study Subjects

Based on pre-clinical data it has been suggested that ARQ 087 may cause a phototoxic reaction in some subjects exposed to the sunlight while being treated with the drug. The amount of ARQ 087 that may be required to cause such reaction is unknown. All subjects should be instructed to avoid sunlight exposure, to use sunscreen to protect exposed areas of

the body (e.g., forehead, nose, lips, and hands), and to immediately report symptoms that may be associated with phototoxic reaction (redness, pruritus, swelling, blister formation).

## 8 SAFETY ASSESSMENTS

### 8.1 Definitions

#### 8.1.1 Adverse Event

An AE is defined as any untoward medical occurrence in a subject or clinical investigational subject administered a pharmaceutical product that does not necessarily have a causal relationship with study-drug treatment. An AE can therefore be any unfavorable and unintended sign (including an abnormal laboratory finding, for example), symptom, or disease temporally associated with the use of a medicinal product, whether or not considered related to the medicinal product.

#### 8.1.2 Serious Adverse Event

An SAE is any adverse experience occurring at any dose that results in any of the following outcomes:

- Death
- Life-threatening
- Requires new inpatient hospitalization defined as a hospital admission lasting > 24 hours (not including emergency room visit without hospital admission), or prolongation of existing hospitalization
- Persistent or significant disability/incapacity
- Congenital anomaly/birth defect
- Other important medical event that may not be immediately life-threatening or result in death or hospitalization but may jeopardize the subject or may require intervention to prevent one of the other outcomes listed above. An important medical event may be considered an SAE based upon appropriate medical judgment.

#### 8.1.3 Unexpected Adverse Event or Serious Adverse Event

An unexpected AE or SAE is one for which the nature or severity of the event is not consistent with the applicable product information, as summarized in the Investigator's Brochure.

#### 8.1.4 Suspected Unexpected Serious Adverse Reaction (SUSAR)

All adverse events that are determined by the Investigator or by the Sponsor as having a reasonable suspected causal relationship to a study drug and that are both unexpected and serious are considered to be SUSARs and are subject to expedited regulatory reporting.

#### 8.1.5 Inpatient Hospitalization

An inpatient hospitalization is a hospital admission that lasts more than 24 hours.

### 8.1.6 Study Drug-related Adverse Event or Serious Adverse Event

Study drug-related AE or SAE is defined as an AE or SAE that is related to the treatment with ARQ 087

### 8.1.7 Further Adverse Event and Serious Adverse Event Defining

Wherever possible, a specific disease or syndrome rather than individual associated signs and symptoms should be identified. However, if an observed or reported sign or symptom is not considered a component of a specific disease or syndrome by the Investigator, it should be recorded as a separate AE.

Laboratory data are to be collected as stipulated in this protocol. Clinical syndromes associated with laboratory abnormalities are to be recorded as appropriate (e.g., diabetes mellitus instead of hyperglycemia).

Scheduled hospitalizations or elective surgical procedures will not be considered as AEs or SAEs.

Prolongation of a scheduled hospitalization can be considered an SAE.

Complications associated with scheduled procedures are considered AEs or SAEs.

Progression of disease is considered an efficacy outcome parameter and should not be captured as an AE or a SAE unless its outcome is death.

Adverse events including SAEs that occur following the execution of the ICF but prior to dosing will not be recorded as AEs or SAEs.

Adverse events including SAEs that occur after subjects receive any anticancer therapy other than the study-defined treatments will not be recorded as AEs or SAEs.

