The hERG IC50 for ARQ 087 was greater than 3 μM. No effect on QT was observed in dogs in the cardiovascular study (60 mg/kg) or in the ECG in the 28-day toxicity study (up to 30/20 mg/kg).

Additionally, the hemodynamic and electrocardiographic effects of ARQ 087 were examined in telemeterized dogs. A slight, transient increase in mean arterial pressure and its components (~15% compared to vehicle) was observed 40 to 120 minutes after dosing with 60 mg/kg ARQ 087. A concomitant increase in heart rate was also noted, and was on average ~20% higher compared to heart rates observed after vehicle dosing within this timeframe. There were no notable effects of ARQ 087 on pulse pressure, PR interval, QRS duration, QTcVDW interval, or arrhythmogenesis.

ARQ 087 was found to have phototoxic potential in the 3T3 Neutral Red Uptake Phototoxicity Test.

Transient effects on clinical chemistry such as increased glucose levels and phosphorous levels were observed in rats and/or dogs in shorter duration 7-Day repeat dose toxicity studies and may be characteristic of FGFR kinase inhibitors.

Based on the findings from the 4-week toxicity studies, the rat is considered as the more sensitive of the two species and will be evaluated for purposes of estimating a safe starting dose for a First in Human (FIH) study conducted in subjects with advanced malignancies. As described in the ICH guidance document: *S9 Nonclinical Evaluation for Anticancer Pharmaceuticals*, a safe human starting dose based on assessment of toxicity in rodent species is 1/10 of the severely toxic dose in 10% of the animals (STD 10). The STD 10 for ARQ 087 was determined to be 50 mg/kg/day, however, due to the need to sacrifice the 50 mg/kg/day animals between Days 12 and 14 of the dosing phase (except those designated for recovery), the 15 mg/kg dose was used to select the safe starting dose in humans. From this dose, the Phase 1 starting dose is calculated to be 9 mg/m^2/day or 15.3 mg/day (BSA 1.7). For the purpose of this FIH study the starting dose is suggested to be 25 mg every other day (QOD) to conform to available capsule dosage strengths (25 and 100 mg) and minimize capsule consumption burden for subjects.

In summary, the pre-clinical data support that ARQ 087 has the potential to exert significant anti-tumor effects on human tumors driven by oncogenic FGFR with an acceptable therapeutic window.

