#### 4.5 Dose-Limiting Toxicity

Dose-limiting toxicities will be determined during the first four weeks/28 days (first cycle) of Treatment Period 2 (Cohorts 1-4) or during Cycle 1 (Cohort 5 and all subsequent cohorts). A DLT is defined by the occurrence of any of the following toxicities related to ARQ 087 within the first 28 days of continuous treatment (Treatment Period 2 or Cycle 1 of Continuous Dosing) and graded according to the Common Terminology Criteria for Adverse Events (CTCAE) version 4.03:

- Grade 4 anemia
- Grade 4 neutropenia
- Grade 4 thrombocytopenia
- Grade 3 neutropenia with fever ( $\geq 38^{\circ}\text{C}/100.4^{\circ}\text{F}$ )
- Grade 3 neutropenia lasting longer than 7 days despite optimal treatment
- Grade 3 thrombocytopenia in the presence of bleeding
- $\geq$  Grade 3 hyperglycemia (fasting blood glucose  $> 250$  mg/dL or non-fasting  $> 500$  mg/dL) requiring insulin (uncontrolled with metformin)
- $\geq$  Grade 3 non-hematological toxicity of any duration, except for the following:
  - Nausea, vomiting, or diarrhea responding to optimal medical management within 48 hours
  - Alopecia
- Any other toxicity that in the view of the Investigator represents a clinically significant hazard to the subject

**Note:** During the dose escalation phase, if the subject experienced a DLT, such subject should be permanently discontinued from the treatment.

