## 8.6 Grading of Severity

Each AE or SAE will be graded for severity according to NCI CTCAE (version 4.03). The criteria can be found at <http://ctep.cancer.gov/reporting/ctc.html>.

For AEs not listed in the NCI CTCAE version 4.03, a similar grading system should be used as follows:

- Grade 1 Mild AE
- Grade 2 Moderate AE
- Grade 3 Severe AE
- Grade 4 Life-threatening or disabling AE
- Grade 5 Death

For AEs that can be described by the NCI CTCAE guidelines, the NCI CTCAE Grade 4 (life-threatening or disabling AE) is assessed based on unique clinical descriptions of severity for each AE, and these criteria may be different from those used for the assessment of AE seriousness. An AE assessed as Grade 4 based on the NCI CTCAE grades may or may not be assessed as serious based on the seriousness criteria.

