5.4.7 Analyses of Safety Variables

All analyses for the safety variables will be performed on safety population. Safety variables include adverse events, laboratory parameters, vital signs, ECOG performance status, 12-lead ECG and physical exams.

Descriptive statistics will be calculated for quantitative safety data, frequency counts and percentages will be compiled for classification of qualitative safety data. All percentages will be calculated based on the number of subjects in the safety population, unless otherwise indicated. Baseline is defined as the last non-missing value prior to the first dose date or on day 1, unless otherwise noted.

Adverse Events

Adverse events will be evaluated for severity using NCI-CTCAE, version 4.03. AE summaries will include treatment-emergent adverse events (TEAEs).

A TEAE is defined as:

- an AE which is not present prior to the first dose of ARQ 087 and started after taking the study drug during the treatment period or within 30 days after the last dose of the study drug;
- an AE which is present prior to the first dose of ARQ 087 and increased in severity after taking study drug during the treatment period or within 30 days after the last dose of study drug;
- an AE which is considered study drug-related regardless of the start date of the event.

All TEAEs will be coded using Medical Dictionary for Regulatory Activities (MedDRA[®]) Version 15.1 and summaries will be presented by system organ class and preferred term. Separate TEAE summaries will be generated for the following categories:

- All TEAEs
- Severe TEAEs (Grade 3 or higher)
- SAEs
- TEAEs related to study drug
- TEAEs leading to treatment discontinuation
- TEAEs leading to treatment interruption
- TEAEs leading to treatment interruption then dose reduction
- TEAEs resulting in death
- TEAEs listed according to maximum severity
- TEAEs classified as DLTs

TEAEs will be summarized by presenting the number and percentage of subjects having at least one TEAE in each system organ class and preferred term. A subject with multiple occurrences of the same TEAE will be counted only once in the AE category.

Separate TEAE summaries will be presented by system organ class, preferred term, and maximum CTCAE 4.03 grade. A subject with multiple CTCAE grades for the same TEAE will be summarized under the maximum CTCAE grade recorded for the event.

Laboratory Test

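### Protocol 8.1.7 uses hyperglycemia as its example of a finding to record under a syndrome term, so the SAP's preferred-term tables can split one anticipated toxicity over two rows

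*Protocol*

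**What the plan says.** Protocol 8.1.7 sets a general preference for diagnoses: "Wherever possible, a specific disease or syndrome rather than individual associated signs and symptoms should be identified". It limits that preference: a sign or symptom that "is not considered a component of a specific disease or syndrome by the Investigator, it should be recorded as a separate AE". For laboratory findings it adds: "Clinical syndromes associated with laboratory abnormalities are to be recorded as appropriate (e.g., diabetes mellitus instead of hyperglycemia".

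Elsewhere the plan treats glucose as a toxicity of interest:

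- Protocol 4.5 has a separate DLT bullet for "Grade 3 hyperglycemia (fasting blood glucose" above a stated cut-off, with a second cut-off for non-fasting values and a requirement for insulin. It applies at that grade or higher.
- Protocol 1.6 reports that "increased glucose levels and phosphorous levels were observed in rats and/or dogs", calls these effects transient, places them in 7-day studies, and says they may be characteristic of the drug class.
- Protocol 6.6 and SAP 3.2.3 list glucose as a pharmacodynamic factor.

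SAP 5.4.7 tabulates the number and percentage of subjects "having at least one TEAE in each system organ class and preferred term". Its text defines no grouped term for glucose events.

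**The concern.** The one example chosen to illustrate the diagnosis-over-finding rule is a toxicity that the same protocol names as dose-limiting. It speaks of one term instead of the other, so it points to replacement, not addition. Two investigators seeing the same glucose rise could enter different terms, and the preferred-term tables would then report the two subjects in different rows.

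Safety is the primary objective in both documents, and a reader looking for the glucose signal will go to the hyperglycemia row. If that row depends on site habits in choosing terms, it is not a reliable incidence figure. The TEAE tables are also the only ones that break events down by relatedness, seriousness, and treatment interruption or discontinuation.

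**Working it through.** The plan states no hyperglycemia rate, so there is no figure of its own to reproduce. The check is mainly a comparison of texts.

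**1. Can the terms diverge?** Yes. Protocol 8.1.7 allows the syndrome term where a syndrome is present and leaves the decision to the investigator. Protocol 3.2 excludes only uncontrolled diabetes, so subjects with controlled diabetes may enrol. In them a glucose rise is most easily attributed to an existing disease.

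**2. Does the SAP text bring the terms back together?** No. SAP 5.4.7 counts by system organ class and preferred term. A subject recorded only under diabetes mellitus is not in the hyperglycemia row of any TEAE table.

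**3. Do the laboratory outputs fill the gap?** Only in part. SAP 5.4.4 summarises glucose at baseline, at each later measurement and as change from baseline. SAP 5.4.7 adds a shift table of CTCAE grade for CTCAE-specified laboratory tests, without naming glucose. Neither depends on the adverse event term. However:

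- Neither carries causality, seriousness or action taken.
- SAP 5.3 restricts post-baseline analyses to scheduled visits and, within a visit, to the last value.
- Protocol 6.4 asks for fasting chemistry samples, whereas the DLT bullet also has a non-fasting cut-off.

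**4. Does the DLT rule depend on the term?** No. The bullet in Protocol 4.5 rests on glucose value, grade and insulin need. The same list also covers "Grade 3 non-hematological toxicity of any duration, except for the following" a short list of exceptions, again at that grade or higher, and any other toxicity the investigator considers a significant hazard.

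**5. Does the grade change?** Possibly. Protocol 8.6 says: "For AEs not listed in the NCI CTCAE version 4.03, a similar grading system should be used as follows", followed by a generic five-step severity scale. Whether that scale would apply depends on whether the syndrome term is listed in CTCAE 4.03, which the documents do not show. The generic scale could also give a higher grade.

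**6. Scale, on assumed values only.** Let *p* be the true proportion with a glucose event and *s* the share of those subjects recorded only under the syndrome term. The hyperglycemia row then shows *p* × (1 − *s*), a relative shortfall of *s*. Take 60 subjects (the upper planned size of the Expanded Cohort) and assume *p* = 20%, so 12 subjects. Intervals are exact 95% (Clopper-Pearson).

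| Assumed share *s* | Subjects in row (rounded) | Row % | 95% interval |
|---|---|---|---|
| 0 | 12 | 20.0 | 10.8 to 32.3 |
| 10% | 11 | 18.3 | 9.5 to 30.4 |
| 25% | 9 | 15.0 | 7.1 to 26.6 |
| 50% | 6 | 10.0 | 3.8 to 20.5 |

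At *s* = 50%, an assumed *p* of 10% shows as 5.0% (3 of 60) and an assumed *p* of 30% as 15.0% (9 of 60). No document supports any of these values of *p* or *s*. The table shows how the mechanism works and does not estimate its size. At shares up to 25% the shift is well inside the sampling uncertainty of a cohort this small. A pooled row restores 12 of 60 whatever *s* is.

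**The case against.** The strongest reply is that 8.1.7 does not order sites to replace hyperglycemia. It speaks of clinical syndromes, says to record them as appropriate, and keeps an unattributed finding as its own event. An isolated, transient glucose rise, which is the pattern described in Protocol 1.6, would stay hyperglycemia. This stands: the rate *can* be split; it is not necessarily split.

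Nor are events lost. One recorded as diabetes mellitus still appears in its own row of every TEAE table that applies to it, and the glucose summaries do not change. This also stands. It does not restore a single incidence figure, because a reader would have to know to look in both rows and could not simply add them: a subject may be in both.

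A pooled row or a term convention might also exist in the SAP's table shells or the eCRF completion guidelines, neither of which is visible in the text available. That limits the finding to the SAP's text.

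Finally, preferring diagnoses to component signs is the protocol's general rule. Agreed, and it need not change. Only the choice of example is at issue.

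**Conclusion.** This is a small, real weakness in reporting. A stated recording rule can make the hyperglycemia incidence row depend on the investigator's choice of term, in a trial whose primary objective is safety. The direction for that row is downward. The amount cannot be quantified from the documents. The conclusion assumes that at least some investigators apply the example and that no pooled row exists outside the SAP's text.

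Three stronger readings may tempt a reader, and the documents do not support them:

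- **That DLTs would be missed or escalation decisions distorted.** The DLT criteria do not use the recorded term, and no missed DLT is shown.
- **That the event leaves the glucose grading scale and is under-graded, with effects on the dose modification table.** This depends on CTCAE content that the documents do not give, and the direction is not fixed. Protocol Table 7.1 acts on the grade of a toxicity, not on its preferred term.
- **That incidence is understated by a particular percentage.** Every such figure rests on an assumed event rate and an assumed recoding share.

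Sample size and the planned efficacy analyses are not affected.

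**What to change.** **Protocol 8.1.7:** delete the hyperglycemia example, so that the section no longer conflicts with the term used for the DLT in 4.5. The general preference for diagnoses can stay.

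**SAP 5.4.7:** pre-specify one pooled row in the all-TEAE, Grade 3 or higher and related-TEAE tables. List the preferred terms by name under the MedDRA version the SAP already specifies (hyperglycemia, blood glucose increased, diabetes mellitus and similar terms). Count each subject once, at the maximum recorded grade. Fix the list before database lock.

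The cost is one deleted phrase and one extra row, which will overlap the individual preferred-term rows and needs a footnote saying so. If data collection is already complete, the SAP row alone repairs the incidence count; recorded grades would stay as entered. Neither change touches a treatment rule.

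I would not go further and require both terms for every episode, or extend the rule to phosphate. Double recording runs against the protocol's own preference for diagnoses, and the pooled row makes both steps unnecessary.
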